#### Symptom assessment

	Present at First Visit	Date Resolved
--	-------------------------------	----------------------

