## **2. OBJECTIVES AND ENDPOINTS**

### **2.1 PRIMARY OBJECTIVE(S)**

This study seeks to demonstrate that the laboratory can mitigate respiratory virus transmission in underserved populations by using laboratory data to identify communities at risk for increase vial activity (hot spots) and intervening with a test-to-treat model provides increased access to influenza diagnostics and treatment in vulnerable and underserved communities.

1. The hot-spot frequency and hot spot score trend will be measured for each census tract to determine if the screen and treat intervention has an impact on reducing hot spot identification or hot spot score.
  - a. Following each mobile intervention, we will evaluate the hot spot score for the census tracts receiving a mobile screen and treat intervention and SVI-matched census tract not receiving an intervention for 14-days following the screen and treat intervention.
  - b. Patients will receive a follow-up phone call 14-days following their initial screening visit to assess patient and household symptoms and the socioeconomic impact of their test result and treatment access.

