All subjects eligible for Xofluza will receive patient education and counseling on drug information, adherence, side effects, and other patient educational materials, as appropriate. All subjects eligible for influenza antiviral therapy, but having contraindications to the therapy, or do not wish to use the therapy will be referred to their primary care provider, provider, or clinic for further evaluation.

Subjects testing positive for SARS-CoV-2 will be preferred by the pharmacist to the subjects' primary care provider, provider, or clinic for further medical assessment and follow-up, if appropriate. Subjects testing negative for all targets (SARS-CoV-2 and Influenza A&B) with a high index of suspicion for influenza, will be referred by the pharmacist to the subjects' primary care provider, provider, or clinic for further medical assessment and follow-up, if appropriate. All subjects will receive a follow-up call 14-days following the study visit to assess their symptom resolution and the impact of their illness on their well-being (Appendix 1).

The mobile testing unit will be deployed a minimum of 2 times per week following the determination of the influenza season by the New Mexico Department of Health. We expect to screen 50-100 patients per week for the duration of the influenza season (approximately 12 weeks) for a total of 600-1,2000 patients. With an anticipated 10% positivity rate for influenza, we expect at least 5-10 patients per week to be eligible for treatment for a total of 60-120 subjects eligible over the course of the study. All subjects will be provided a survey to evaluated their ability to access respiratory virus testing and their acceptance of and trust in using a mobile unit for access to treatment and therapeutics. Patients positive for SARS-CoV-2 will be counseled on options for treatment and follow up for COVID-19 infection. All subjects enrolled in the study will receive a follow-up phone call 14-days following the initial screening visit.

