## **6.2 PLANNED EFFICACY EVALUATIONS**

This is an observational study of the population. Individual patient efficacy will not be assessed.

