#### **Fever or chills**

#### **Cough**

#### **Sore throat**

#### **Runny or stuffy nose**

#### **Muscle or body aches**

#### **Headaches**

#### **Fatigue (tiredness)**

#### **Did your illness cause you (or household members) to miss**

	Self	Household Member	Days Missed	Was there any additional requirement to allow return to activity? (I.e., required days at home or negative test)
Work				
School				
Grocery	 YES	 No		
Shopping	 YES	 No		
Faith-based activity	 YES	 No		
Fitness	 YES	 No		
Other:	 YES	 No		
Name				

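### The 14-day follow-up form cannot distinguish a symptom still present at the call from a missing date, and it cannot separate the patient's lost days from the household's when both are affected

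*Combined protocol and SAP*

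**What the plan says.** Section 2.1 places the call under the primary objective, as item 1b: "Patients will receive a follow-up phone call 14-days following their initial screening visit to assess patient and household symptoms and the socioeconomic impact". Section 3.1 says all subjects are called at 14 days "to assess their symptom resolution and the impact of their illness on their well-being" and refers to Appendix 1 for the form. Section 3.2 repeats that purpose and schedules no follow-up visits.

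The symptom table on the form is headed "Present at First Visit" and "Date Resolved" and lists seven symptoms, from fever or chills to fatigue. No heading provides for a symptom that is still present, not known or not asked. The activity table is introduced by "Did your illness cause you (or household members) to miss". It has separate columns for self and household member but a single column for days missed, and no visible not-applicable option for work or school.

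Section 6 gives no rule for these fields. Section 6.2 states: "Individual patient efficacy will not be assessed". Section 6.5 covers only the hot spot score.

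**The concern.** The form is the instrument named for symptom resolution and socioeconomic impact, and the 14-day call is the last contact planned with each subject. About 600 to 1,200 people are expected to receive it. Two of its fields do not record what a later summary would need.

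First, a duration observed for 14 days needs a status as well as a date. Without the status, a symptom that outlasts the window looks the same as one whose end date was not obtained. Whoever tabulates the form must decide what a blank means, and the result changes with that decision.

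Second, the form asks about household illness elsewhere, so rows in which both the patient and others lost days are to be expected. In those rows a single number of days cannot be divided afterwards. What is at stake is how far item 1b can be answered. The comparison of census tracts is not at stake.

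**Working it through.** **No figure to reproduce.** The plan states no symptom duration, days-lost estimate or rule for blanks. The check is therefore a reading of the form, followed by an illustration of how far the unstated rule can move a result.

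**Inputs.** The follow-up horizon is 14 × 24 = 336 hours (Section 2.1). Median durations come from Section 1.2.1.1: 53.7 hours (Xofluza) and 80.2 hours (placebo) in otherwise healthy patients, and 102.3 hours (placebo) in high-risk patients. These are influenza composite endpoints, borrowed only to set a scale. The shape of the distribution and the share of missing dates are assumptions.

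**Rule A: blanks dropped, all resolved symptoms dated.** Let M be the true median and the distribution exponential. The share unresolved at the call is u = 2^(−336/M). The median among dated symptoms is M × [1 − log2(1 + u)].

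- M = 53.7: u = 0.013; median 52.7 hours (2% short)
- M = 80.2: u = 0.055; median 74.0 hours (8% short)
- M = 102.3: u = 0.103; median 87.9 hours (14% short)

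With a lognormal distribution and log-SD s, u = 1 − Φ(ln(336/M)/s), and the median among dated symptoms is M × exp(s × z), where z is the standard normal quantile at (1 − u)/2. For M = 102.3:

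- s = 0.8: u = 0.069; median 95.5 hours (7% short)
- s = 1.2: u = 0.161; median 80.2 hours (22% short)

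**Rule B: every blank read as ongoing at the call.** Let m be the share of dates missing at random. With the exponential distribution, the apparent median is −M × log2[1 − 0.5/(1 − m)].

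| True median (hours) | m = 5% | m = 10% | m = 20% |
|---|---|---|---|
| 53.7 | 57.9 | 62.8 | 76.0 |
| 102.3 | 110.3 | 119.7 | 144.8 |

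In relative terms these are 8%, 17% and 42% too long. At m = 0 the formula returns M, so rule B has no bias when every blank really is an ongoing symptom.

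**With a recorded status.** If ongoing symptoms are marked, none of the resolved ones lacks a date, and ongoing symptoms are censored at 336 hours, the case is rule B with m = 0. The assumed median is recovered.

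**Days missed.** Suppose a patient loses 3 days and two household members lose 2 days each. The entry can be 3 (own days) or 3 + 2 × 2 = 7 (everyone). If both the self and household columns are marked, the form does not show which was meant. If only one is marked, the days belong to that party, although several household members would still share one number.

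**The case against.** The strongest reply is that no estimate of duration or days lost is planned. Section 6 confines efficacy to the hot spot score, so there is no stated result for the form to bias. That is right, and it limits the weight of the point. It does not remove it, because item 1b still says the call assesses these things, and the form is what the call will leave behind.

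A reader might infer that symptom duration will be biased short. The documents do not support that. It follows only if blanks are dropped, and no section says they will be. Reading blanks as ongoing gives no bias or a bias towards long.

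A reader might infer that days lost can never be attributed, or that people who do not work make the mean too low. Neither follows. The self and household columns allow attribution when only one is marked. Zero days for a non-worker is the correct entry if the target is days per respondent. It misleads only if the target is days per worker, and the plan names neither target.

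A reader might also infer that first-visit symptoms rest on recall and that nothing can be repaired later. The symptoms are examined at the visit (Section 4.5.3), and the case report form confirms that the physical assessment was documented, so that column can be taken from source. A caller could also write that a symptom is ongoing in the date field, although no instruction asks for it.

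Finally, the table layout was disturbed in the text available. The column headings are clear, but the exact use of the cells beneath them is not. The point therefore rests on the headings alone.

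**Conclusion.** The point holds in a limited form. On its headings, the form leaves a blank resolution date ambiguous and gives one number of days where two or more parties may have lost time. Any duration summary would depend on a rule the plan does not state, and the direction of error depends on that rule.

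The size cannot be derived from the documents. Under the assumptions shown, dropping blanks makes the median about 2% to 22% too short. Reading blanks as ongoing makes it 8% to 42% too long when 5% to 20% of dates are missing. These are illustrations, not predictions. Most of those called are expected to be influenza-negative (80% to 90%, at the 10% to 20% positivity in Section 6.1), and the documents give no symptom durations for them.

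The matter is one of data capture for a descriptive item. The hot spot comparison and the sample size do not change. The revision is worth making because it is cheap and has to precede the calls.

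**What to change.** Revise the 14-day form before the first call:

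1. For each symptom, record one status: resolved, with date; still present at the call; or not known.
2. State in Section 6 that any duration summary treats symptoms still present as censored at the call date (for example, Kaplan-Meier), and report the number not known separately.
3. Split days missed into the patient's own days and household days, say whether household days are summed over members, and add a not-applicable option for work and school.
4. Fill the first-visit symptom column from the visit record.

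The cost is a one-page form revision, a sentence or two in Section 6 and a slightly longer call (about a minute, as an estimate).

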#### **Fever or chills**

#### **Cough**

#### **Sore throat**

#### **Runny or stuffy nose**

#### **Muscle or body aches**

#### **Headaches**

#### **Fatigue (tiredness)**

#### **Did your illness cause you (or household members) to miss**

	Self	Household Member	Days Missed	Was there any additional requirement to allow return to activity? (I.e., required days at home or negative test)
Work				
School				
Grocery	 YES	 No		
Shopping	 YES	 No		
Faith-based activity	 YES	 No		
Fitness	 YES	 No		
Other:	 YES	 No		
Name				

**Appendix 2**  
**Safety Reporting Fax Cover Sheet**

*A Member of the Roche Group*

**SAFETY REPORTING FAX COVER SHEET**

**GENENTECH SUPPORTED RESEARCH**

AE / SAE [contact]

Genentech Study Number	
Principal Investigator	
Site Name	
Reporter name	
Reporter Telephone #	
Reporter Fax #	

Initial Report Date	[DD] / [MON] / [YY]
Follow-up Report Date	[DD] / [MON] / [YY]

Subject Initials (Enter a dash if patient has no middle name)	[ ] - [ ] - [ ]
--	-----------------

SAE or Safety Reporting questions, contact Genentech Drug Safety: [contact]

PLEASE PLACE MEDWATCH REPORT or SAFETY REPORT BEHIND THIS COVER SHEET

## **Appendix 3** **FDA MedWatch 3500 Form**

This form is included in the study start-up zip file to be sent to sites via email.

## **Appendix 4** **Management Criteria for Abnormal Liver Function Tests**

Management Criteria for Abnormal Liver Function tests have been designed to ensure patient safety and evaluate liver event etiology (see Guidance for Industry Drug-Induced Liver Injury: Premarketing Clinical Evaluation, FDA: 2009; available from: <https://www.fda.gov/downloads/Guidances/UCM174090.pdf>).

### **Abnormal Liver Chemistry Criteria**

The investigator or subinvestigator must review study patient laboratories to identify if any levels meet the following criteria:

- AST or ALT  $>5 \times$  upper limit of normal (ULN)
- AST or ALT  $>3 \times$  ULN and total bilirubin (TBL)  $>2 \times$  ULN or INR  $>1.5$ , if INR is measured
- AST or ALT  $>3 \times$  ULN with signs or symptoms compatible with hepatitis or hypersensitivity (e.g., fatigue, nausea, vomiting, right upper quadrant pain or tenderness, jaundice, fever, rash, eosinophilia [ $>5\%$ ])

### **Action to be Taken by Investigator**

If any abnormal liver chemistry criterion is met, the investigator or subinvestigator must do the following:

- Patients must be instructed to discontinue study medication immediately.
- Following the initial observed elevation, every effort should be made to have the patient return to the clinic within 72 hours (if already discharged from hospital) to repeat liver function chemistries and for further hepatic evaluation.
- Every effort should be made to have the patients monitored 2 to 3 times per week until liver function chemistries (i.e., ALT, AST, ALP, TBL) resolve, stabilize per investigator judgement, or return to within the normal range or to baseline levels.
- Consultation with a specialist, such as a hepatologist, and liver imaging (i.e., ultrasound, magnetic resonance imaging [MRI], computerized tomography) should be considered for worsening laboratory values or symptoms.
